#### Risks and Discomforts:

Potential adverse effects of monitoring sleep studies are minimal. Allergic reaction to electrode placement has been reported but the frequency of these reports is not known. If the participant does experience an allergic reaction to either the placement of electrodes or the sensor patch to the forehead the Research Technologist, shall terminate the study and recording will be terminated.

## Data Analysis, Safety, Confidentiality and Compensation:

Demographic data will be presented with descriptive analysis. Sleep Study data will be scored as per AASM (American Academy of Sleep Medicine) standards and will be tested for normal distribution with respect to prediction of neck and head roll angles normalizing the AHI (Apnea Hypopnea Index). Normalizing AHI or reducing to sufficient levels to decrease the symptoms of untreated POSA will be documented for each subject. The results of this pilot study may be used to power a larger trial.

With respect to confidentiality, a unique identification number designed to protect the identity of participant will be used to identify the participant on report forms, recruitment logs, data forms or other report containing information. Each participant will sign a HIPAA authorization

permitting the release of protected health information to the sponsor, the investigative team, and regulatory authorities.

Safety maintenance at the Sleep Center during the overnight visit shall be maintained in accordance Policies and Procedures currently in place at the Sleep Center located at [name].

Participants will be compensated for travel expenses and time commitment. Participants will be compensated \$50.00 for the screening visit and up to \$400.00 for each overnight sleep study they complete.

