## The Effect of Head Pitch and Roll Rotation Independent of Torso Position on the AHI in Positional Obstructive Sleep Apnea

## 1. Background and Study Aim

The prevalence of Obstructive Sleep Apnea (OSA) can be as high as 9% within the general population. A subset of OSA, described as Positional Obstructive Sleep Apnea (POSA), defined operationally as apneas occurring during specific positions while asleep, occurs predominantly in the supine position. Approximately 30% of obstructive sleep apnea (OSA) patients have supine-predominant OSA.(2) The patients diagnosed with obstructive sleep apnea that position dependent are at least twice as severe when sleeping supine. In one study, the prevalence of POSA was as high as 50% in patients diagnosed with mild sleep apnea (AHI, 5-15/h) and as low as 7% in patients diagnosed with severe sleep apnea (AHI > 30/hr) (1). Results from another study of 1170 adults Asian patients conducted over a span of four years, from 2004 through 2008, demonstrated that the presence of POSA is almost three-fourths of the patients and that the AHI is the most dominant factor for determining positional dependency, followed by BMI. (3)

It has been hypothesized that POSA may also occur independent of torso position but is affected solely by head position, independent of supine. A review of drug-induced endoscopy in OSA which is predominantly performed in the supine position concluded that head rotation improves upper airway collapse during this procedure in supine position. (4). Thus while the treatment of POSA has generally been directed at limiting sleeping in the supine position without regards to effects of head position, rotating the head away from the 90 degree position might alleviate the "crush force" seeking to close the upper airway. This study seeks to verify whether rotation of the head while sleeping in the supine position during polysomnography affects the calculated AHI. Head rotation will be defined in terms of degree rotation from a 90 degree starting position (head position aligned with supine position) and rotating the head from right to left defining the movement in terms of a widening angle from 0 degrees to 90 degrees through 180 degrees, thus reducing the AHI. A secondary aim is to develop an algorithm that can predict whether a specific degree of head rotation can be assigned to a percentage reduction in AHI.

The diagram below, provided by the sponsor, illustrates this maneuver:

[figure not shown]

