## Study Procedures:

- Subject (participant) how are eligible will be scheduled for a daytime screening session at the Sleep Center located at [name] with either the Study Coordinator or Staff Research Technologist. Following the screening visit and signed consent, qualified participants shall be asked to complete an overnight sleep study (polysomnogram).
- Following the screening visit, participant will be scheduled for an overnight sleep study and participant will arrive at scheduled time, generally between the hours of 7:00 PM and 8:30 PM.
- Research Technologist greets patient, verified individual personal information and matches the assigned Participant Clinical Data Binder (PCD) including the assigned study number.
- 4. Research Technologist shall complete the demographic section of the PCD and explain the sleep study to the participant.
- 5. Research Technologist shall attach electrodes as per Sleep Systems Research Montage and escort participant to assigned sleep room and will further explain to the participant the "process" of gathering sleep study data (i.e. calibrations, use of call button and the system that will be utilized to rotate the head as per protocol.)

- Research Technologist will attach forehead sensor to the most level surface of forehead without getting too close to the eyes with medical tape. Small foam wedges may be necessary under the sensor to adjust for calibration. Research Technologist will confirm the pitch and roll angles to be 90 degrees +/- 5 degrees.
- 7. Participant is allowed to watch Television or read until "Lights Out" as determined by the Research Technologist.
- 8. Once recording has commenced the Research Technologist shall complete the scoring forms as per protocol. Once the baseline AHI for POSA is verified (generally about 2 hours following sleep) Research Technologist shall enter the Sleep room and initiate neck roll maneuvers, utilizing wedge pillows as follows:
  - a) 30 degrees on right for 45 minutes.
  - b) 60 degrees on right for 45 minutes
  - c) 90 degree (head and neck aligned with supine torso) for 45 minutes
  - d) 120 degrees to left for 45 minutes
  - e) 150 degree to left for 45 minutes.

The goal is to normalize AHI (<5).

9. If no calculated AHI indicative of POSA (>5) is achieved the participant will be awakened at 7:00 AM and discharged from Sleep Center.

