#### APPENDIX A

# **Sleep Study Score Sheet**

This score sheet represents the ideal baseline information that Sleep Systems would like to see for the sleep study. All numbers in the table should be replaced with actual values

Measured Head Pitch	Measured Head Roll	Pillow Angle (°) or Style	Torso Position	Start Time	Stop Time	Measured Duration	Measured AHI Events	Meası Oxyg Satura
Angle(°)	Angle(°)	Used				(Min.)	/Hour	(%
70-90	90	Flat	Supine	10:00P	11:00P	60	25	90
70-90	90	Flat+Towell	Side	11:00P	12:00P	60	25	90
70-90	15 or 165	15	Side	12:00A	1:00A	60	5	100
70-90	15 or 165	15+Towell	Supine	1:00A	2:00A	60	5	100
70-90	0 or 180	Flat	Side	2:00A	3:00A	60	17.5	96
70-90	45 or 135	45	Side or Supine	2:00A	3:00A	60	17.5	96

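### The sleep-data analysis targets the head-roll angle that normalizes AHI, which some participants will not have and others will have more than once; the secondary aim's percentage reduction by angle exists for everyone

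*Protocol*

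**What the plan says.** The protocol's section on data analysis, safety, confidentiality and compensation gives one analysis for the sleep-study data: after standard scoring, they "will be tested for normal distribution with respect to prediction of neck and head roll angles normalizing the AHI". The next sentence adds a record per person: "Normalizing AHI or reducing to sufficient levels to decrease the symptoms of untreated POSA will be documented for each subject". No number is attached to a sufficient reduction.

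Study Procedures, step 8, sets the threshold: "The goal is to normalize AHI (<5". It schedules five 45-minute settings, from "30 degrees on right for 45 minutes" through 60, 90 and 120 degrees to "150 degree to left for 45 minutes".

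The secondary aim in section 1 (Background and Study Aim) is put differently: to "develop an algorithm that can predict whether a specific degree of head rotation can be assigned to a percentage reduction in AHI".

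Appendix A shows one illustrative night. It has AHI 25 at roll 90, 17.5 at 45/135, 5 at 15/165 and 17.5 at 0/180, and its numbers are marked for replacement by actual values. The study enrols up to 10 participants and may be used to power a larger trial.

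**The concern.** The analysis section and the secondary aim describe different quantities. Percentage reduction at a given angle can be computed for any participant with a baseline AHI and completed settings. The angle that normalizes AHI can be computed only for a participant who falls below 5 somewhere, and it is not a single value for a participant who does so at more than one setting. The protocol assigns no value in either case.

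An analysis of normalizing angles, carried out as worded, therefore leaves out the participants in whom rotation worked least well. With at most 10 people, each one left out matters, and any summary of the remainder is conditional on success. That is a poor basis for planning a later trial.

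**Working it through.** The protocol states no expected normalization rate, so there is no figure to reproduce. The check asks how often a normalizing angle would fail to exist.

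**Inputs from the protocol**
- Threshold: AHI < 5 (Study Procedures, step 8).
- Rotated settings: 30, 60, 120 and 150 degrees, 45 minutes (0.75 h) each.
- Example AHI in Appendix A: 25 at 90 degrees, 17.5 at 45/135, 5 at 15/165.

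**Assumptions (none in the protocol)**
- AHI falls linearly between the Appendix A values, by degrees from 90. The 0/180 row is left out.
- The same proportional curve holds at other peak AHI values.
- Events are independent Poisson counts, with the full 45 minutes asleep.

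**Step 1: AHI at the scheduled settings, peak 25**
- 60/120 (30 degrees from 90): 25 − (30/45) × 7.5 = 20.0, or 0.80 of peak.
- 30/150 (60 degrees from 90): 17.5 − (15/30) × 12.5 = 11.25, or 0.45 of peak.

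Neither is below 5. The lowest example value is exactly 5, at 15/165, which is not a scheduled setting.

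**Step 2: peak below which a setting has expected AHI < 5**
- 30/150: 5/0.45 = 11.1.
- 60/120: 5/0.80 = 6.25.
- With a straight line from 90 to 15 instead, the 30/150 figure becomes 5/0.36 = 13.9.

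**Step 3: probability that no rotated setting is observed below 5**

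In 0.75 h, AHI < 5 needs at most 3 events (3/0.75 = 4; 4/0.75 = 5.33). Let a = P(≤3 events) at 30/150 and b = P(≤3 events) at 60/120. Then P(none) = (1 − a)² × (1 − b)².

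| Peak AHI | a | b | P(no normalizing angle) |
|---|---|---|---|
| 8 | 0.714 | 0.294 | 0.04 |
| 10 | 0.564 | 0.151 | 0.14 |
| 15 | 0.256 | 0.021 | 0.53 |
| 20 | 0.096 | 0.002 | 0.81 |
| 25 | 0.031 | 0.0002 | 0.94 |

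At a peak of 6 the probability is about 0.005. Counting the 90-degree block as a fifth chance changes little (0.13 instead of 0.14 at peak 10).

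**Step 4: share over a group**

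If peak AHI were uniform, the average share with no normalizing angle (five settings) would be 18% over 5–15, 58% over 5–30 and 85% over 15–30.

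**Step 5: more than one angle**

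Simulating the four rotated settings at peak 10, 53% of normalizers are below 5 at two or more settings.

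**Step 6: effect of restricting to normalizers**

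The assumed reduction at 30/150 is 1 − 0.45 = 55% at every peak. In the simulation, the mean among normalizers only is 59% at peak 10, 64% at peak 15 and 70% at peak 25.

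**The case against.** **The algorithm is not itself defined in two ways.** The analysis section does not mention the algorithm. Its wording could mean deriving an angle from a fitted model, and the Apnea Severity Calculator in the appendix returns a calculated AHI from peak AHI, pitch and roll, which exists for everyone. This is fair. Still, the only sentence on analysing the sleep data names the normalizing angle and does not carry over the reduction-by-angle aim.

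**Non-normalizers are not lost from the record.** Normalization or sufficient reduction is documented for each subject, and the investigator reviews each study for normalization. That stands, but neither gives a non-normalizer a value in the analysis that is named.

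**A reader might infer from Appendix A that most participants would have no normalizing angle.** The documents do not support this. Appendix A is one placeholder profile; it is not monotone (AHI is back to 17.5 at 0/180), and one profile gives no proportion of participants. Section 1 reports positional disease as commonest in mild apnea (AHI 5–15), where the same assumptions give 18% on average.

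**A reader might also infer that the study would report an inflated reduction.** The protocol does not state an analysis of reductions in normalizers only. At peak 25, the 70% describes the 6% who normalize, fewer than one person expected in 10.

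**Handling of such cases could be left to the SAP.** The choice of count model could. The protocol itself, however, fixes the target, and an SAP faithful to it would inherit the difficulty.

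**Conclusion.** The point holds as a defect in the named analysis target. The angle that normalizes AHI is undefined for a participant at 5 or more at every scheduled setting, is not unique for one below 5 at several, and differs from the quantity in the secondary aim. These conclusions follow from the protocol's own wording and need no modelling.

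The size is uncertain. The probability of having no normalizing angle runs from about 0.04 at a peak AHI of 8 to 0.94 at 25, under the interpolation, scaling and Poisson assumptions above. A participant like the Appendix A example would probably be such a case; how many of the 10 would be cannot be said without a baseline AHI distribution. The 59–70% against 55% comparison shows what a normalizers-only summary of reductions would do, not what the protocol plans. The change should be made, because the better target is already among the study's aims.

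**What to change.** In the data analysis section, replace the normalizing angle as the target with the secondary aim's percentage reduction in AHI by degree of rotation.

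- Use the scored events and sleep time at every step 8 setting for every participant, in a repeated-measures model against degrees of roll from 90. One example is a count model with a participant effect and log sleep time as offset. Derive the expected reduction at each angle from the fit.
- Report normalization as a yes/no proportion, with all participants who underwent the roll maneuvers in the denominator.
- If a normalizing angle is reported, record it as not reached where no setting is below 5, and state which angle counts when several are.

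The cost is a change of wording and slightly more analysis, with no added data, participants or procedures. The reported result may be less favourable than one drawn from normalizers alone.

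### The per-subject AHI verdict has an unnumbered symptom-based arm and names no own-participant reference, so it cannot show whether, or by what percentage, head roll changes AHI

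*Protocol*

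**What the plan says.** The protocol's section on data analysis, safety, confidentiality and compensation sets the per-subject outcome: "Normalizing AHI or reducing to sufficient levels to decrease the symptoms of untreated POSA will be documented for each subject". It says the scored sleep data "will be tested for normal distribution with respect to prediction of neck and head roll angles normalizing the AHI", and adds: "The results of this pilot study may be used to power a larger trial".

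The aims are in section 1. The primary aim reads: "This study seeks to verify whether rotation of the head while sleeping in the supine position during polysomnography affects the calculated AHI". The second aim is worded as follows: "develop an algorithm that can predict whether a specific degree of head rotation can be assigned to a percentage reduction in AHI".

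Study Procedures, step 8, gives the numerical target, "The goal is to normalize AHI (<5"), and provides two possible own-participant references. One is the baseline that opens the maneuvers: "Once the baseline AHI for POSA is verified (generally about 2 hours following sleep"). The other is the third of five roll settings: "90 degree (head and neck aligned with supine torso) for 45 minutes". Under step 9, a participant whose AHI does not exceed 5 is not maneuvered. The Appendix A score sheet has columns for angles, pillow, torso position, times, duration, AHI and oxygen saturation. The Apnea Severity Calculator takes the participant's own peak AHI near 90 degrees, but only as the input for a calculated AHI.

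**The concern.** Both aims are contrasts: an effect of rotation and a percentage reduction each need a reference AHI. The stated verdict is not a contrast. Its first arm is an absolute level. Its second is a level that cannot be applied, because it has no number and depends on symptoms that neither the procedures nor the score sheet describes measuring after the maneuvers.

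Two things are at stake. A participant with mild disease may be recorded as normalized when roll did nothing. And the quantity a larger trial would be powered on, the relative change from 90 degrees and its spread between participants, is not among the stated results, although the data for it are collected.

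**Working it through.** The protocol gives no power, effect size or AHI distribution, so there is no stated figure to reproduce. The calculations below are illustrations under labelled assumptions.

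**Inputs.** From the protocol: threshold 5 events/h, 45-minute windows, four rotated settings (30, 60, 120, 150 degrees), a baseline of about 2 hours that must exceed 5, and up to 10 participants. Assumed: Poisson events, independent windows, 45 full minutes of sleep in each, and supine AHI between 6 and 25.

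**1. What below 5 means in one window.** 5 × 0.75 h = 3.75 events, so the label requires 3 events or fewer. The exact 95% CI for 3 events in 45 minutes is 0.8 to 11.7 per hour.

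**2. Label with no roll effect.** p = P(X ≤ 3), X Poisson with mean 0.75 × AHI. If any of the four rotated windows may count (the protocol does not say), the chance is 1 − (1 − p)^4.

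| Supine AHI | Mean events | One window <5 | Any of four <5 |
|---|---|---|---|
| 6 | 4.5 | 34% | 81% |
| 8 | 6.0 | 15% | 48% |
| 10 | 7.5 | 6% | 22% |
| 15 | 11.25 | 0.4% | 1.6% |
| 25 | 18.75 | about 0% | about 0% |

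With an assumed within-night coefficient of variation of 0.3, the one-window figures become 39%, 21%, 11%, 2% and 0.1%.

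**3. Does the baseline gate remove this?** If the gate is more than 5 per hour over 2 hours of supine sleep (assumption), it needs at least 11 events, mean 2 × AHI. It is passed in 65%, 92% and 99% of cases at AHI 6, 8 and 10. Passing the gate and then reading below 5 in one given window has probability 0.65 × 0.34 = 22%, 0.92 × 0.15 = 14% and 0.99 × 0.06 = 6%. The gate thins the mildest cases but does not remove the problem.

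**4. The below-5 arm taken alone, for a true halving.** The mean is 0.375 × AHI. P(X ≤ 3) is 19% at supine AHI 15 (mean 5.625) and 1.6% at 25 (mean 9.375).

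**5. Why the reference must be named.** Simulated participants with no roll effect (baseline log-SD 0.4, between-participant effect SD 0.5 on the log scale, within-night CV 0.3) were kept only if they had 11 or more baseline events. Against that gated baseline, the mean ratio is 0.81–0.83, 0.88–0.89, 0.91–0.94 and 0.97–0.99 at median supine AHI 6, 8, 10 and 15; the ranges reflect repeated simulations. Against the own 90-degree window it is 1.00–1.02. The baseline is selected for being high, so in mild disease it suggests a reduction where there is none.

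**6. The score sheet's sample values.** These are placeholders and show only how the wording would operate. A fall from 25 to 5 is (25 − 5)/25 = 80%, yet 5 is not below 5. A fall from 25 to 17.5 is 7.5/25 = 30%, and the second arm gives no means of classifying it.

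**The case against.** Four objections deserve weight.

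*The participant is already compared with themselves.* A reader might infer that the protocol makes no own-participant comparison. The text does not support that. Maneuvers follow a verified baseline above 5, so normalized already implies a move from above 5 to below it, and the score sheet opens with a flat, supine, 90-degree row. What stands is narrower: the analysis section does not say which own reference applies, and step 5 above shows that the choice matters.

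*A model may sit in the SAP.* A reader might infer that the normality test is the only planned analysis and that the aims therefore go unanalysed. The protocol does not say so, and a SAP may hold the model. Its absence here is not the finding. The test as worded can only be a supportive check, since it estimates neither an effect nor an angle relation.

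*The second arm may catch large falls that stay above 5.* It may. The 19% and 1.6% therefore describe the below-5 arm only. To say that the full verdict misses real reductions goes further than the text allows: its miss rate cannot be computed while the second arm is undefined. Nor can one say that no symptom data exist, because the participant clinical data forms are not reproduced in full; one can say only that no such measure is described.

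*The largest figures are an edge case.* Largely true. The glossary requires total AHI of at least 5 and a halving between supine and non-supine. With supine AHI 6, non-supine AHI at most 3 and supine share w, total AHI is at most 6w + 3(1 − w) = 3(1 + w), which reaches 5 only if w is at least 2/3. With half the night supine, supine AHI must be at least 5/0.75 = 6.7. At 25, the protocol's own sample value, the false-label rate is about zero.

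The score sheet also records AHI, duration, roll angle and torso position by window, so the inputs for a ratio exist whatever label is written. The gap is in the stated outcome, not in data collection.

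**Conclusion.** The point holds in this form. One arm of the stated verdict cannot be applied as written. The other is an absolute level with no named reference, and neither shows whether rotation changes AHI or by what percentage.

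False labels of normalization are confined to about supine AHI 5 to 10: 34% of single windows at 6, falling to 6% at 10 and 0.4% at 15. If any of four windows may count, the figures are 81%, 22% and 1.6%. These rest on Poisson events, full sleep in each window and no roll effect. How many participants fall in that range is unknown, because the protocol gives no AHI distribution. For a non-randomized pilot of up to 10, this is a wording correction that should be made; it does not invalidate the design.

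**What to change.** In the data analysis section:

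- Delete the clause about levels sufficient to decrease symptoms, or replace it with the measured percentage change in AHI.
- Keep AHI below 5 as a descriptive label, reported for each angle with event count and sleep minutes, beside the participant's own 90-degree window and baseline.
- State that the effect of roll is the within-participant ratio (percentage change) of AHI at each rotated angle, torso supine, versus the own 90-degree window, summarized across participants with a 95% CI. Use the baseline as a sensitivity reference only, because it is selected for exceeding 5. The exact estimator may be left to the SAP, and any normality check is supportive.

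**Cost.** Wording and a short calculation, with no new data or procedures. The symptom-based label is lost, and intervals will be wide. The simulation behind this assumed a true ratio of 0.5, n = 10, between-participant SD 0.5 and within-night CV 0.3, with the two windows at equal distance from 90 degrees combined. It used differences in log((events + 0.5)/sleep hours) and a t interval with 9 df. The typical 95% interval is about 0.30–0.87 at supine AHI 15. At AHI 6 it is about 0.27–0.99, or 0.28–0.94 if all 10 participants pass the gate. Fewer evaluable participants would widen these further.
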